1.2.2 Secondary estimand(s)

The four key secondary endpoints defined in the protocol are considered for estimands as below.

1.2.2.1 Secondary estimand 1 : Proportion of responders who can tolerate a single dose of ≥ 1000 mg of peanut protein at Week 12

The secondary estimand 1 is the same as the primary estimand except that “a single dose of ≥ 600 mg (1044 mg cumulative tolerated dose)” is replaced by “a single dose of ≥ 1000 mg (2044 mg cumulative tolerated dose)”.

1.2.2.2 Secondary estimand 2: Proportion of responders who can tolerate a single dose of 3000 mg of peanut protein at Week 12

The secondary estimand 2 is the same as the primary estimand except that “a single dose of ≥ 600 mg (1044 mg cumulative tolerated dose)” is replaced by “a single dose of ≥ 3000 mg (5044 mg cumulative tolerated dose)”.

1.2.2.3 Secondary estimand 3: Maximum severity of symptoms up to and including 1000 mg of peanut protein

This secondary estimand 3 is described by the following attributes:

- **Population:** same as for the primary estimand.
- **Variable:** maximum severity of symptoms occurring at any challenge dose of peanut protein up to and including 1000 mg during the DBPCFC conducted at Week 12. According to CoFAR grading scale of dose-limiting symptoms, symptom severity will be categorized as Mild, Moderate and Severe. Symptom severity for participants who completed DBPCFC without any symptoms will be categorized as “None”.
- **Treatment:** same as for the primary estimand.
- **Handling of intercurrent events:**
 - Discontinuation of treatment or missing more than one dose prior to Week 12: Missing data at Week 12 will be replaced by the maximum severity of symptoms at screening (*composite variable strategy*).

- Intake of rescue medication prior to DBPCFC conducted at Week 12: ignorable (*treatment policy strategy*, reflected in the “Treatment” attribute).
- **Summary measure:** odds ratio comparing the odds of developing less severe symptoms between each ligelizumab dose group and placebo group.

1.2.2.4 Secondary estimand 4: Proportion of responders who can tolerate a single dose of 1000 mg of peanut protein at Week 12 with 8 weeks of placebo followed by 4 weeks of ligelizumab

The secondary estimand 4 provides insight into the treatment effect after one dose of ligelizumab. This secondary estimand is the same as the primary estimand except the following attributes :

- **Variable:** Responder status defined as tolerating a single dose of ≥ 1000 mg (2044 mg cumulative tolerated dose) of peanut protein without dose-limiting symptoms during the DBPCFC conducted at Week 12.
- **Treatment:** the randomized treatment (placebo 8 weeks to ligelizumab 240 mg SCq4w, placebo 8 weeks to ligelizumab 120 mg SCq4w and placebo 16 weeks to ligelizumab 240/120 mg SCq4w) plus rescue medication, if needed.

2 Statistical methods

2.1 Data analysis general information

The statistical analysis of the study will be performed by [REDACTED] a designated Contract Research Organization (CRO) following this document. SAS version 9.4 will be used to perform all analyses.

There are two planned analyses before the final database lock, in addition to the DMC analyses. The details of these analyses are provided in the [Section 2.13](#) below.

An independent DMC will conduct periodic monitoring of safety data and emerging risk/benefit. Interim reports to the DMC will be generated by an independent statistical group not involved in the conduct of the trial. Statistical Analysis Plan for the DMC analyses will be prepared separately.

Categorical data will be summarized as frequencies and percentages. For continuous data, mean (geometric mean for non-normal distributed variables), standard deviation, median, 25th and 75th percentiles, minimum and maximum will be presented.

2.1.1 General definitions

2.1.1.1 Study treatment

The study treatment includes investigational drug QGE031 and placebo. The following abbreviated treatment groups will be used as the headers in the tables.

- QGE031 240 mg q4w
- QGE031 120 mg q4w
- Placebo 8 wks – QGE031 240 mg

- Placebo 8 wks – QGE031 120 mg
- Placebo 16 wks – QGE120 or 240 mg q4w*

* In the efficacy analysis outputs, placebo 16 wks switch will be labelled as “placebo group” for simplicity.

In addition, for most of safety summaries, the following abbreviated treatment groups under different pooling period will be used as the headers in the tables.

- Placebo-controlled pool up to Week 8 (QGE031 240 mg vs. QGE031 120 mg vs. three Placebo arms combined)
- Placebo-controlled pool up to Week 16 (QGE031 240 mg vs. QGE031 120 mg vs. Placebo 16 wks – QGE120 or 240 mg)
- Entire study period up to Week 68 (combined three arms with QGE031 240 mg vs. combined three arms with QGE 120 mg)

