2.1.1.3 Baseline definition

In general, baseline is defined as the last measurement before the first dose of study treatment. Details on calculation of baseline for PRO measures is provided in [Section 2.10](#).

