2.2 Analysis sets

The Randomized Analysis Set (RAS) consists of all randomized participants, regardless of whether or not they receive a dose of study drug. Participants will be analyzed according to the treatment they are assigned to.

The Full Analysis Set (FAS) comprises all participants who received at least one dose of study treatment. According to the intent to treat principle, participants will be analyzed according to the treatment they have been assigned to during the randomization procedure. Mis-randomized patients (mis-randomized in IRT) will be excluded. Mis-randomized patients are defined as cases where IRT contacts were made by the site either prematurely or inappropriately prior to confirmation of the patient's final randomization eligibility and no study medication was administered to the patient. FAS will be used for all efficacy variables, unless otherwise stated.

The Safety Set (SAF) includes all participants who received at least one dose of study treatment whether or not being randomized. Participants will be analyzed according to the treatment they received, where treatment received is defined as the randomized/assigned treatment if the participant took at least one dose of that treatment or the first treatment received if the randomized/assigned treatment was never received. The safety set will be used in the analysis of all safety variables.

[REDACTED]

[REDACTED]

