2.4 Treatments (study treatment, rescue medication, concomitant therapies, compliance)

2.4.1 Study treatment / compliance

The duration of exposure in weeks to each treatment group will be summarized using descriptive statistics.

Duration of exposure to study treatment will be calculated as the number of weeks between the first dose date and the last dose date exposed to that treatment over the specified period (Duration of exposure = (date of last known study treatment – date of first known study treatment + 28)/7).

In addition, the number of doses, total cumulative dose and number of missed doses will be presented. Categorical data will be summarized as frequencies and percentages. For continuous data, mean, standard deviation, median, 25th and 75th percentiles, minimum and maximum will be presented.

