2.7 Safety analyses

All safety endpoints (i.e. AEs, laboratory data, vital signs, and ECG) will be summarized by treatment for all participants on the safety set. In addition, subgroup analysis by age (12-17 years, 18-55 years) will be evaluated for most of the safety endpoints listed in this section. The safety analyses will be performed by the treatment groups for the three pooling periods as described in Section 2.1.1.1, unless otherwise specified.

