2.7.1 Adverse events (AEs)

Unless otherwise specified, summaries will include treatment-emergent adverse events (TEAEs) only. Treatment emergent adverse events are defined as events started after the first dose of study treatment and within 16 weeks after the last study treatment, or events present prior to the first dose of study treatment but increased in severity based on preferred term within 16 weeks after the last study treatment. All events that the investigator classifies as reactions associated to the DBPCFC or SPT will not be included in reporting of treatment-emergent AEs and may be reported separately. The number and percentage (with exact binomial 95% CIs) of participants with TEAEs will be summarized in the following ways:

- by treatment, primary system organ class and preferred term.
- by treatment, primary system organ class, preferred term and maximum severity.
- by treatment, Standardized MedDRA Query (SMQ) and preferred term.

Separate summaries will be provided for study treatment-related adverse events, death, serious adverse events, other significant adverse events leading to discontinuation and TEAEs with potential cause of accidental exposure or ingestion. If a participant reported more than one AE with the same preferred term, the AE with the greatest severity will be presented. If a participant reported more than one AE within the same primary system organ class, the participant will be counted only once with the greatest severity at the system organ class level, where applicable.

For the legal requirements of ClinicalTrials.gov and EudraCT, two required tables on TEAEs which are not SAEs with an incidence greater than a certain threshold based on the final database and on TESAEs and SAEs suspected to be related to study treatment will be provided by system organ class and PT on the safety set population.

If for a same patient, several consecutive AEs (irrespective of study treatment causality, seriousness and severity) occurred with the same SOC and PT:

- a. a single occurrence will be counted if there is ≤ 1 day gap between the end date of the preceding AE and the start date of the consecutive AE
- b. more than one occurrence will be counted if there is > 1 day gap between the end date of the preceding AE and the start date of the consecutive AE

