2.7.1.1 Exposure-Adjusted Incidence Rate

The crude incidence rate is defined as the percentage of participants with a specific adverse event divided by the total number of participants in each study group.

Due to expected differences in exposure and follow-up due to varied duration of study participation between participants, adverse event incidence rates will be provided as “exposure adjusted AE incidence rates” in addition to the crude incidence.

The EAIR is defined as the number of participants with a specific event divided by the total exposure-time among the participants in the study group. That is, the EAIR is calculated as:

$EAIR = n / \sum t_i$, where n is the number of participants having the i^{th} type event, and t_i is a participant's exposure time and defined as the shortest of the following:

1. time to the first episode of the i^{th} type event (if the event occurs),
2. time to the end of observation period, or
3. duration of study treatment plus the 16-week washout period (approximately corresponding to five half-lives) after last treatment dose

The total exposure time of all participants in a treatment group is $\sum t_i$. The EAIR is interpreted as the number of events occurring in a population per unit time. The exact Poisson 95% confidence interval for the EAIR will be provided as well, where an exact $100*(1-\alpha)\%$ confidence interval will be derived as follows (Garwood 1936, Sahai and Khurshid 1993):

- Lower confidence limit $L = \frac{0.5C_{\alpha/2,2n}}{\sum t_i}$ for $n>0$, 0 otherwise,
- Upper confidence limit $U = \frac{0.5C_{1-\alpha/2,2n+2}}{\sum t_i}$,

where $C_{\alpha,k}$ is the α th quantile of the Chi-square distribution with k degrees of freedom.

Whenever applicable, exposure adjusted incidence rates will be provided for the type as below:

1. TEAE: Primary SOC level, PT level

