2.7.3 Laboratory data

The descriptive summary statistics (mean (95% CI), median, first and third quartiles, minimum and maximum) for change from baseline to each study visit and maximum/minimum value will be presented. These descriptive summaries will be presented by test group, laboratory test and treatment group. Change from baseline will only be summarized for participants with both baseline and post baseline values for quantitative parameters, and the maximum/minimum value could come from post-baseline scheduled, unscheduled or premature discontinuation visits. For categorical parameters, frequencies by categories at each visit will be summarized.

The laboratory values below Lower Level of Quantification (LLOQ) or above Upper Level of Quantification (ULOQ) will be imputed as LLOQ or ULOQ in the summary tables, respectively. The numerical part of the reported result will be treated as the actual LLOQ or ULOQ. These laboratory values will be displayed in listings using the standard unit with the reported sign (“<” or “>”).

For selected laboratory parameters, abnormalities occurring at any time-point from scheduled, unscheduled and premature discontinuation visits considering all post-baseline on-treatment data will be summarized. Where normal ranges are available, abnormalities in laboratory data may be listed by, participant, and visit/time.

The number of participants with worsening abnormality during the study will be summarized by treatment. A case is considered as worsening abnormality if the value at baseline and at least one post-baseline value during the study is worse than baseline.

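### The Week 68 safety pool has only ligelizumab-dose columns, so placebo lead-in events and time are counted as ligelizumab, and no rule clearly removes participants who never received it

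*SAP*

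**What the plan says.** SAP Section 2.1.1.1 states that study treatment covers both ligelizumab and placebo. It then sets out three safety pools. The Week 8 and Week 16 pools have a placebo column. The third is "Entire study period up to Week 68 (combined three arms with QGE031 240 mg vs. combined three arms with QGE 120 mg"). Under SAP Section 2.7, "The safety analyses will be performed by the treatment groups for the three pooling periods", unless otherwise specified.

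The rules that feed the pools are these:

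- Treatment-emergent events (SAP 2.7.1) are "events started after the first dose of study treatment and within 16 weeks after the last study treatment", plus earlier events that worsen.
- Time in the exposure-adjusted incidence rate (EAIR, SAP 2.7.1.1) is capped, among other limits, at "duration of study treatment plus the 16-week washout period (approximately corresponding to five half-lives) after last treatment dose".
- Baseline (SAP 2.1.1.3): "In general, baseline is defined as the last measurement before the first dose of study treatment".
- Safety-set assignment (SAP 2.2) uses the assigned treatment, or "the first treatment received if the randomized/assigned treatment was never received".
- Duration of exposure (SAP 2.4.1) is measured between "the first dose date and the last dose date exposed to that treatment over the specified period".

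Under SAP Section 1.1, participants who had not reached Week 12 Part 2 at the halt end treatment at that visit. Those already past it receive no drug at their next visit. Protocol Section 12.5.2 says that placebo-arm data after the switch are summarised separately. The SAP does not repeat this, and SAP Section 4 does not list it as changed.

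**The concern.** Three arms per dose can only mean the always-active arm, the 8-week switch arm and half of the 16-week switch arm. Because every clock starts at the first dose of study treatment, a switch-arm participant's placebo weeks belong to a ligelizumab column. The SAP then treats the same event in two ways. A Week 3 event in the 8-week switch arm for 240 mg is a placebo event in the Week 8 pool and a 240 mg event in the Week 68 pool.

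The halt adds a second problem. A 16-week-arm participant stopped before Week 16 dosing never receives ligelizumab, and neither does a switch-arm participant who discontinues before the switch. The safety-set fallback does not say whether the assigned treatment of a sequence arm is the sequence or its ligelizumab part. This pool also has no placebo column to move such a participant into.

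Laboratory, ECG and vital-sign changes are affected too. SAP 2.7.3 says "Change from baseline will only be summarized for participants with both baseline and post baseline values for quantitative parameters", and in the switch arms that change spans the placebo phase.

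At stake is the description of longer-term ligelizumab safety: the absolute rates and changes in each column.

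**Working it through.** **The plan's own figure.** Protocol 12.8.2.1 gives 243 participants per dose at N = 486. With 2:2:2:2:1 allocation and the 16-week arm split 1:1, 486 × (2/9 + 2/9 + 1/18) = 108 + 108 + 27 = 243, which matches. At N = 211 a column holds 46.9 + 46.9 + 11.7 = 105.5 participants. Of these, 58.6 (55.6%) began on placebo.

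**Person-time.** Column weights are 2 : 2 : 0.5 (always-active, 8-week switch, 16-week switch), total 4.5. L and P are weighted ligelizumab and placebo weeks.

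- All followed to Week 68: L = 2×68 + 2×60 + 0.5×52 = 282; P = 2×8 + 0.5×16 = 24.
- All stop at Week 12 with 16 weeks of follow-up, and the 16-week arm never switches: L = 2×28 + 2×20 = 96; P = 2×8 + 0.5×28 = 30.
- Half-and-half mix: L = 189; P = 27.

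The second set adds the 15% discontinuation before Week 12 from SAP 3.1. I assume it is spread evenly over last doses at Weeks 0, 4 and 8 (5% each), with 16 weeks at risk after the last dose. For the Week 68 case:

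- always-active L = 0.85×68 + 0.05×(16+20+24) = 60.8
- 8-week arm L = 0.85×60 + 0.05×16 = 51.8; P = 0.85×8 + 0.05×(16+20+8) = 9.0
- 16-week arm L = 0.85×52 = 44.2; P = 0.85×16 + 0.05×60 = 16.6
- Weighted totals: L = 247.3, P = 26.3

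The Week 12 case works the same way.

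| Scenario | L | P | Placebo share f | Never exposed |
|---|---|---|---|---|
| Week 68, no dropout | 282 | 24 | 7.8% | 0% |
| Mix, no dropout | 189 | 27 | 12.5% | 5.6% |
| Stop at Week 12, no dropout | 96 | 30 | 23.8% | 11.1% |
| Week 68, 15% dropout | 247.3 | 26.3 | 9.6% | 6.1% |
| Mix, 15% dropout | 168.25 | 28.85 | 14.6% | 10.8% |
| Stop at Week 12, 15% dropout | 89.2 | 31.4 | 26.0% | 15.6% |

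Never exposed with dropout, Week 68 case: (2×0.10 + 0.5×0.15)/4.5 = 6.1%. Week 12 case: (2×0.10 + 0.5)/4.5 = 15.6%. The three dropout rows correspond to about 6, 11 and 16 of 105 participants.

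**Effect on the EAIR.** For drug-to-placebo rate ratio r, the pooled rate divided by the ligelizumab-only rate is 1 − f(1 − 1/r). This ignores censoring at the first event, so it is a rare-event approximation.

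- r = 2: 0.961, 0.938, 0.881 without dropout; 0.952, 0.927, 0.870 with it.
- r = 1: 1.000 throughout.
- r = 0.5: 1.078, 1.125, 1.238 without dropout; 1.096, 1.146, 1.260 with it.

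Protocol 4.5 reports injection site reactions of 28.6% (ligelizumab high-dose group) and 5.2% (placebo) in an asthma study. Treating 5.2/28.6 = 0.18 as a rate ratio gives 0.94 at f = 7.8% and 0.81 at f = 23.8%. This is only an illustration, because those figures are incidences.

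**Effect on crude percentages.** For rare events, relative to exposed participants only, the ratio is [(L + P/r)/4.5] / [L/(4.5 − never)], with never in weight units.

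- r = 1: 1.085, 1.079, 1.167 without dropout; 1.039, 1.045, 1.142 with it.
- r = 2: 1.043, 1.012, 1.028 without dropout; 0.989, 0.968, 0.993 with it.

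**The case against.** The strongest reply has five parts.

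- **Five-arm headers.** SAP 2.1.1.1 also lists five arm-level headers, and the pools serve most, not all, safety summaries. That is true, but a switch-arm header still does not split that arm's time into placebo and ligelizumab.
- **Placebo data appear elsewhere.** The Week 8 and Week 16 pools show the scheduled lead-ins under placebo. This stands, and it means those data are not lost. It does not take them out of the ligelizumab columns of the third pool.
- **Treatment-specific dates.** SAP 2.4.1 could be read into the EAIR cap. The link is not written, and it would not reach the event counts in 2.7.1. Restricting only the denominator would leave placebo-phase events over ligelizumab-only time.
- **The protocol rule may still apply by default.** It may, but the two columns do not implement it.
- **Size.** At a rate ratio of 2 the crude percentages move only from 3.2% too low to 4.3% too high. That is small beside the SAP Table 3-3 interval of 0.1% to 3.5% for a 1% event at n = 211. This also stands. In addition, the all-stop-at-Week-12 scenario is a limiting case, since some participants had already passed Week 12 or completed Week 52 at the halt.

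**Conclusion.** The point holds. Followed literally, the SAP counts placebo lead-in events and time under ligelizumab in its only pool beyond Week 16, and it has no clear rule for participants who never switched.

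The percentages are scenario values, not bounds, because the documents give no halt-group sizes. The truth should lie between the two end cases. Full follow-up is unrealistic because SAP Section 4 expects few participants to reach Week 52, and universal stopping at Week 12 is the opposite limit. The rate ratios of 2, 1 and 0.5 and the even spread of dropout are assumptions.

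The consequence is limited. The pool is descriptive, both placebo-controlled pools are clean, and the 240 mg and 120 mg columns have the same randomised composition. What is distorted is each column's absolute rates and changes as a description of ligelizumab safety. This should be fixed before the tables are produced.

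**What to change.** 1. In SAP 2.1.1.1, define the third pool as the ligelizumab-exposed period, limited to participants with at least one ligelizumab dose.
2. In 2.7.1 and 2.7.1.1, start event counting and EAIR time for this pool at the first ligelizumab dose (Day 1, Week 8 or Week 16) and end both 16 weeks after the last. An event already present at that first dose counts only if it then worsens.
3. In 2.1.1.3, 2.7.3 and 2.7.4, use the last value before the first ligelizumab dose as this pool's baseline. On the visit schedule, the laboratory baseline becomes Week 4 for the 8-week arms and Week 12 for the 16-week arm. The ECG baseline stays at Screening Visit 1 for the 8-week arms and becomes Week 12 for the 16-week arm.
4. Show placebo-phase events and never-switched participants separately under placebo, and state in 2.2 how treatment received applies to the switch arms.
5. Keep the protocol 12.5.2 rule by giving always-active, post-switch and total sub-columns within each dose. If only the total is kept, list that as a change in SAP Section 4.

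The cost is wording in those sections, plus a period-start date and a second baseline flag in the analysis datasets. No new data are needed. The pool will hold fewer participants and less person-time, and laboratory and ECG baselines will lie at different distances from the first ligelizumab dose across arms.

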2.1.1.2 Study day

Study day will be defined as the number of days since the date of first dose of study treatment. The date of first dose of study treatment will be defined as Day 1 and the day before the first dose of study treatment will be defined as Day -1.

Therefore, for a particular date, study day will be calculated as follows:

For dates on or after the first dose date of study treatment, study day will be calculated as [Assessment date – Date of first dose of study treatment + 1]. For dates prior to the first dose date of study treatment, study day will be calculated as [Assessment date – Date of first dose of study treatment].

2.1.1.3 Baseline definition

In general, baseline is defined as the last measurement before the first dose of study treatment. Details on calculation of baseline for PRO measures is provided in [Section 2.10](#).

